13.1.2. Part 2: Expansion Cohort

For Part 2, hypothesized response rates are provided in Section 13.2.2 below. In this case, a test that the ORR is less than or equal to the null hypothesis rate versus the ORR is greater than or equal to the alternative rate will be performed using the stopping rules provided in Section 13.6.2. Descriptive statistics will be used to describe the observed ORRs at the RP2 dose used in the expanded cohorts.

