13.2.2. Part 2: Expansion Cohort

Dose escalation will be used to establish the RP2 dose for GSK2857916. Once the RP2 dose is confirmed, at least 15 and up to 40 subjects in total will be enrolled into the MM cohort using decision rules defined in [Table 17](#). The sample size and stopping rules are based on the methodology of Lee et al. [[Lee, 2008](#)]. The assumptions underlying the design are detailed below.

The null hypothesis is:

$$H_0: p \leq 20\%$$

The alternative hypothesis is:

$$H_A: p \geq 40\%$$

For the MM expansion cohort, starting with 15 subjects and allowing for a maximum sample size of 40, this design will have a type I error rate (α) of 0.075 and 89.8% power. The trial is not designed to stop early for efficacy, but is designed to stop early for futility if the predictive probability of success is less than 5%. The type I error rate, power, and predictive probability of success to stop early for futility were derived from explicitly stating the minimum and maximum sample size, allowing for the futility stopping rate to range from 5% to 20% within the predictive probability design software, and selection of the optimizing criterion as the maximization of power under the alternative hypothesis. The Bayesian prior probability used in determining the design was Beta (0.25, 0.75), a distribution with a mean response rate of 25%. Under the null hypothesis, if the true response rate is 20%, the expected sample size of the design is 23.4 subjects and probability of early termination (PET) is 88.9%. Under the alternative hypothesis, if the true response rate is 40%, the expected sample size of the design is 38.6 subjects and probability of early termination (PET) is 8.5%.

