13.6. Interim Analysis

13.6.1. Part 1

While no formal interim analysis is planned for Part 1, safety, pharmacokinetic and pharmacodynamic marker data will be examined on an ongoing basis to support dose escalation decisions. Prior to determining the GSK2857916 dose for the next cohort enrolled, exploratory analysis will be conducted to assess the relationship of GSK2857916 dose levels with safety, PK and PD parameters using all data from available cohorts. For more details of the dose escalation procedure, see Section 3.3.

13.6.2. Part 2

The methodology utilized is based on the predictive probability of success if enrollment continues to 40 subjects [Lee, 2008]. The predictive probability design is similar to a Green-Dahlberg design in that it allows for early stopping for futility. The differences are that the predictive probability design allows for evaluation of stopping rules as often as after each subject, rather than at only two stages. While the two designs have similar type I and type II error rates, the probability of early termination is greater with the predictive probability design. In this particular study, we will stop only for futility and evaluate the stopping rules once approximately 15, 22, and 30 subjects are evaluable (though additional futility looks are also controlled for if necessary). A subject is considered evaluable if they are in the all treated population and have had at least two post baseline disease assessments.

For the MM expansion cohort, response data will be reviewed once approximately 15, 22, and 30 subjects are evaluable and the number of overall responses (PR, VGPR, CR, and sCR) observed will be compared with the stopping rules provided in Table 17 below.

Table 17 Futility Stopping Region

Number of Evaluable Subjects	Number of Overall Responses												
	0	1	2	3	4	5	6	7	8	9	10	11	>11
15	Shaded	Shaded	Shaded										
16	Shaded	Shaded	Shaded										
17	Shaded	Shaded	Shaded										
18	Shaded	Shaded	Shaded	Shaded									
19	Shaded	Shaded	Shaded	Shaded									
20	Shaded	Shaded	Shaded	Shaded									
21	Shaded	Shaded	Shaded	Shaded									
22	Shaded	Shaded	Shaded	Shaded	Shaded								
23	Shaded	Shaded	Shaded	Shaded	Shaded								
24	Shaded	Shaded	Shaded	Shaded	Shaded								
25	Shaded	Shaded	Shaded	Shaded	Shaded	Shaded							
26	Shaded	Shaded	Shaded	Shaded	Shaded	Shaded							
27	Shaded	Shaded	Shaded	Shaded	Shaded	Shaded							
28	Shaded	Shaded	Shaded	Shaded	Shaded	Shaded							

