29	Shaded	Shaded	Shaded	Shaded	Shaded	Shaded	Shaded						
30	Shaded	Shaded	Shaded	Shaded	Shaded	Shaded	Shaded						
31	Shaded	Shaded	Shaded	Shaded	Shaded	Shaded	Shaded						
32	Shaded	Shaded	Shaded	Shaded	Shaded	Shaded	Shaded	Shaded					
33	Shaded	Shaded	Shaded	Shaded	Shaded	Shaded	Shaded	Shaded	Shaded				
34	Shaded	Shaded	Shaded	Shaded	Shaded	Shaded	Shaded	Shaded	Shaded	Shaded			
35	Shaded	Shaded	Shaded	Shaded	Shaded	Shaded	Shaded	Shaded	Shaded	Shaded			
36	Shaded	Shaded	Shaded	Shaded	Shaded	Shaded	Shaded	Shaded	Shaded	Shaded			
37	Shaded	Shaded	Shaded	Shaded	Shaded	Shaded	Shaded	Shaded	Shaded	Shaded	Shaded		
38	Shaded	Shaded	Shaded	Shaded	Shaded	Shaded	Shaded	Shaded	Shaded	Shaded	Shaded		
39	Shaded	Shaded	Shaded	Shaded	Shaded	Shaded	Shaded	Shaded	Shaded	Shaded	Shaded	Shaded	
40	Shaded	Shaded	Shaded	Shaded	Shaded	Shaded	Shaded	Shaded	Shaded	Shaded	Shaded	Shaded	Shaded

Note: The shaded regions are the specific regions for stopping the study for futility. For instance, if there are 4-5 or fewer responses in 25 subjects, then the predictive probability for success will be less than the futility criterion, 5.0%, and the study will be stopped.

In addition to the considering the recommendations of the futility analyses, final decisions on stopping enrolment in the MM cohort will depend on the totality of the data collected. Examples of consideration of the totality of the data include, further investigation of the clinical activity of subgroups of subjects based on their BCMA expression levels and evaluation of the quality of responses (including sCR, CR and Clinical Benefit Rate, as defined in [Appendix 1](#)). Should the recommendation to stop for futility be disregarded in favor of a decision to continue the trial based on the totality of the data, the overall type I error rate of the expansion phase will be inflated.

No interim analyses will be performed on the BCMA+ lymphomas cohort; though consideration would be given to closing the cohort should the enrollment be stopped in the MM cohort.

If necessary, a subject may be replaced if they are deemed to be Lost to Follow-Up (LTFU) or they have withdrawn due to a toxicity deemed to not have been related to GSK2857916.

Subjects will not be replaced when they discontinue the study due to: Progression (symptomatic or otherwise), toxicity related to GSK2857916, or lack of efficacy.

Other administrative interim analyses may be performed if needed.

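### As rendered in the protocol text, Table 17 shades one response too many at 33 to 39 subjects and every column at 40, against the plan's own 5% rule; the planned looks are unaffected

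*Protocol*

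**What the plan says.** Section 13.2.2 sets up a predictive-probability design for the MM cohort, "starting with 15 subjects and allowing for a maximum sample size of 40". The null response rate is 20% and the alternative 40%, the prior is Beta(0.25, 0.75), and enrolment stops for futility if the predictive probability of success falls below 5%. It claims a type I error "of 0.075 and 89.8% power". It adds that "if the true response rate is 20%, the expected sample size of the design is 23.4 subjects" with an 88.9% probability of early termination (PET), and that "if the true response rate is 40%, the expected sample size of the design is 38.6 subjects" with a PET of 8.5%.

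Section 13.1.2 says that the test of the response rate "will be performed using the stopping rules provided in Section 13.6.2". Section 13.6.2 plans looks at about 15, 22 and 30 evaluable subjects, "though additional futility looks are also controlled for if necessary". Table 17 then gives one row for each number of evaluable subjects from 15 to 40, with columns for 0 to 11 responses and '>11'. Its note says "The shaded regions are the specific regions for stopping the study for futility" and explains, for an example at 25 subjects, that at or below the bound "then the predictive probability for success will be less than the futility criterion, 5.0%, and the study will be stopped".

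No section states in words how many responses out of 40 count as success.

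**The concern.** Table 17 is where sections 13.1.2 and 13.2.2 send the reader for the decision rule. From row 33 on, the bound rises faster than a 5% rule would make it: 7 at 32 subjects, 8 at 33, 9 at 34. Row 40 shades all 13 columns, so no count of responses is left outside the futility region. If the original table looks like this, an extra look late in enrolment could recommend stopping a cohort that the plan's own rule would continue. A reader looking to row 40 for the final criterion would find none.

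**Working it through.** **Inputs** (sections 13.2.2 and 13.6.2): prior Beta(0.25, 0.75); maximum N = 40; stop if predictive probability < 0.05; p = 0.20 and 0.40; looks possible from 15 to 39. The success count R is not stated and has to be inferred.

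**Formula.** With x responses in n subjects and m = 40 − n still to come, the number of further responses Y is beta-binomial with parameters m, 0.25 + x and 0.75 + n − x. The predictive probability is PP(n, x) = P(Y ≥ R − x). The bound at n is the largest x with PP < 0.05. Operating characteristics follow by exact binomial recursion.

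**Step 1: reproduce the plan's figures.** Look after every subject from 15 to 39, with bounds from the 5% rule:

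| R | alpha (p = 0.20) | power (p = 0.40) |
|---|---|---|
| 11 | 0.141 | 0.944 |
| **12** | **0.0754** | **0.8975** |
| 13 | 0.038 | 0.838 |
| 14 | 0.017 | 0.746 |

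R = 12 also gives PET 0.8885 and 0.0849, and expected sample size 23.42 and 38.64. These agree with the stated 0.075, 89.8%, 88.9%, 8.5%, 23.4 and 38.6 to rounding. Of the four cut-offs tried, only 12 fits.

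**Step 2: compare Table 17 with the rule at R = 12.** Rows 15 to 32 match in all 18 cases, including close ones: PP(18, 3) = 4.90% and PP(25, 5) = 4.99%. The planned looks at 15, 22 and 30 have bounds 2, 4 and 6 in both. Rows 33 to 39 differ:

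| n | Highest shaded count | PP there | Bound under the 5% rule | PP there |
|---|---|---|---|---|
| 33 | 8 | 8.2% | 7 | 1.2% |
| 34 | 9 | 20.7% | 8 | 4.2% |
| 35 | 9 | 12.5% | 8 | 1.7% |
| 36 | 9 | 6.0% | 8 | 0.4% |
| 37 | 10 | 18.6% | 9 | 1.8% |
| 38 | 10 | 7.4% | 9 | 0 |
| 39 | 11 | 28.1% | 10 | 0 |

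Two rows can be checked by hand:
- At 11 of 39, one more response gives 12 of 40, so PP = (0.25 + 11)/(1 + 39) = 11.25/40 = 28.1%.
- At 10 of 38, both remaining subjects must respond, so PP = (10.25/39) × (11.25/40) = 7.4%.

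**Step 3: row 40.** At 40 the outcome is known: 0 to 11 is not a success and 12 or more is. The '>11' column should therefore be open. It is shaded.

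**Step 4: consequence if the rendered bounds were used,** still counting 12 or more of 40 as success:

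| Looks | Bounds | alpha | power | PET (20% / 40%) |
|---|---|---|---|---|
| Every subject, 15 to 39 | 5% rule | 7.5% | 89.8% | 88.9% / 8.5% |
| Every subject, 15 to 39 | as rendered | 6.1% | 87.6% | 93.9% / 12.4% |
| 15, 22, 30 plus one look in 33 to 39 | as rendered | 6.9% to 7.8% | 89.2% to 90.5% | – |

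**The case against.** Four points weigh against a stronger claim.

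- **The original may be right.** Shading is a visual feature, and in the protocol text it survives only as a word in each cell. The discrepancy is a constant shift of one column from row 33 on, which fits a slip in reading the table as well as an author's slip. A '>11' column has a purpose only if row 40 leaves it open, and section 13.2.2's figures come from the correct bounds. Against this, rows 32 to 40 each keep all 13 cells and rows 15 to 32 read without error. The text alone cannot settle it, so the point has to be conditional.
- **A reader might infer that the trial cannot succeed, or that alpha and power are wrong.** The documents do not support either. Table 17 is a futility region, and at 40 there is no enrolment left to stop. The prior, maximum N, alpha and power in section 13.2.2 single out 12 of 40 among the cut-offs tried, and the stated operating characteristics reproduce.
- **A reader might infer that the interim decisions are compromised.** They are not. The three planned looks have the correct bounds, and looks after 32 subjects are only provided for if needed.
- **The table does not act alone.** Section 13.6.2 makes stopping depend also on the totality of the data and allows the futility recommendation to be overridden. Response rate is a secondary endpoint, and section 13.5.1 says no formal testing will be done.

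All four stand as limits on severity. None reconciles rows 33 to 40, as rendered, with the 5% rule in the table's own note.

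**Conclusion.** The point holds conditionally and is minor. As rendered, rows 33 to 39 are each one response above the plan's 5% rule, with predictive probabilities of 6.0% to 28.1% in the extra cells, and row 40 shades the success column.

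The effect reaches only optional looks after 32 subjects and the reading of the final criterion. With a look after every subject, power falls by about 2 points (89.8% to 87.6%) and alpha falls from 7.5% to 6.1%, so the error would not inflate the type I error. With the three planned looks and one late look, power stays between 89.2% and 90.5%.

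This rests on success being at least 12 of 40, which is inferred from the stated operating characteristics, and on the original shading matching the protocol text, which remains to be checked.

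**What to change.** Compare rows 33 to 40 of Table 17 with the shading in the original document. If they match the text:

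- correct the upper bounds to 7 at 33 subjects, 8 at 34 to 36, 9 at 37 and 38, 10 at 39, and 11 at 40;
- leave '>11' unshaded at 40;
- state in section 13.6.2 that success is at least 12 responses in 40.

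Printing the bounds as numbers would remove the dependence on shading. The cost is eight table rows and one sentence; sample size, planned looks and stated operating characteristics do not change. If the original shading is already correct, the rows need no change, and the sentence on the success count would be a useful clarification only.

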13.7. Key Elements of Analysis Plan

Data will be listed and summarized according to the GSK reporting standards, where applicable. Complete details will be documented in the Reporting and Analysis Plan (RAP). Any deviations from, or additions to, the original analysis plan described in this protocol will be documented in the RAP and final study report.

As it is anticipated that accrual will be spread thinly across centers and summaries of data by center would be unlikely to be information, data from all participating centers will be pooled prior to analysis.

All data up to the time of study completion/withdrawal from study will be included in the analysis, regardless of duration of treatment.

As the duration of treatment for a given subject will depend on efficacy and tolerability, the duration of follow-up will vary between subjects. Consequently there will be no imputation for missing data.

Demographic and baseline characteristics will be summarized.

13.7.1. Anti-Cancer Activity Analyses

The All Treated Population will be used for anti-cancer activity analyses. Since this is a Phase I study, anti-cancer activity will be evaluated based on clinical evidence and response criteria. If data warrant, the response data will be summarized by dose level. Correlation analysis will be conducted to explore any relationship between the tumor response based on either the International Myeloma Working Group Uniform Response Criteria (for subjects with MM; see [Appendix 1](#)) or the Response Criteria for Malignant Lymphoma (for subjects with lymphomas, refer to [Appendix 2](#)). Full details will be specified in the Reporting and Analysis Plan (RAP).

13.7.2. Safety Analyses

The All Treated Population will be used for the analysis of safety data. All serially collected safety endpoints (e.g. laboratory tests, vital signs, electrocardiogram [ECGs]) will be summarized according to the scheduled, nominal visit at which they were collected and across all on-treatment time points using a “worst-case” analysis. Complete details of the safety analyses will be provided in the Reporting and Analysis Plan (RAP).

13.7.2.1. Extent of Exposure

The number of subjects administered study treatment will be summarized according to the duration of therapy.

13.7.2.2. Adverse Events

Adverse events (AEs) will be coded using the standard MedDRA and grouped by system organ class. Adverse events (AEs) will be graded by the investigator according to the National Cancer Institute- Common Toxicity Criteria for Adverse Events (NCI-CTCAE), (version 4).

Events will be summarized by frequency and proportion of total subjects, by system organ class and preferred term. Separate summaries will be given for all AEs, treatment-related AEs, serious adverse events (SAEs) and AEs leading to discontinuation of study treatment. Adverse events (AEs), if listed in the NCI-CTCAE (version 4) will be summarized by the maximum grade. Otherwise, the AEs will be summarized by maximum intensity.

Characteristics (e.g. number of occurrences, action taken, grade, etc) of the following AEs of clinical interest will be summarized separately: corneal events, hematologic toxicities (including but not limited to thrombocytopenia and neutropenia), infusion related reaction etc. Details will be provided in the RAP.

The incidence of deaths and the primary cause of death will be summarized.

13.7.2.3. Clinical Laboratory Evaluations

Hematology and clinical chemistry data will be summarized using frequencies and proportions according to National Cancer Institute-Common Toxicity Criteria for Adverse Events (NCI-CTCAE) (Version 4.0). The evaluation of clinical laboratory tests will focus on selected laboratory analytes from the hematology and blood chemistry panel.

Descriptive statistics (mean, standard deviation, median, range) will be used to summarize observed laboratory values and change from baseline in observed value at each scheduled visit, as appropriate.

The worst-case- toxicity grade in hematology and chemistry result during the treatment will be summarized. Shift tables from baseline to the worst toxicity grade during treatment will be provided for each laboratory analyte.

Further details will be provided in the Reporting and Analysis Plan (RAP).

13.7.2.4. Immunogenicity Analyses

For each subject, the results and titers of anti-GSK2857916 binding antibodies will be listed for each assessment time point. The frequency and percentage of subjects with positive and negative results will be summarized for each assessment time and overall for each subject by dose cohort.

13.7.2.5. Other Safety Measures

Data for vital signs, electrocardiograms (ECGs), and echocardiograms (ECHOs) will be summarized based on predetermined criteria identified to be of potential clinical concern (PCI). For continuous variables, these summaries will include sample size, mean, median, standard deviation, minimum, and maximum. For categorical variables, the summaries will include frequencies and corresponding percentages. Further details will be provided in the Reporting and Analysis Plan (RAP).

13.7.3. Pharmacokinetic Analyses

13.7.3.1. Raw Plasma Concentrations

Linear and semi-logarithmic individual plasma concentration-time profiles and mean and median profiles (when applicable) by GSK2857916 dose and schedule will be plotted for both GSK2857916 (intact and total) and cys-mcMMAF in Part 1.

In Part 2, individual model-predicted GSK2857916 plasma concentration-time profiles, observed concentrations in individual subjects and population predicted plasma concentrations provided by NONMEM (non-linear mixed effects modelling), will be presented graphically by subject (semi-log plot) and by treatment (linear and semi-log plots).

Plasma concentrations of GSK2857916 (intact and total) and cys-mcMMAF will be listed for each subject and summarized by planned time point, dose cohort and schedule in Part 1 and Part 2.

Derived Plasma Pharmacokinetic Parameters

Pharmacokinetic analysis will be the responsibility of the CPMS Department, QSci, GSK.

In Part 1 of the study, plasma GSK2857916 concentration-time data will be analyzed by non-compartmental methods using WinNonlin. Calculations will be based on the actual sampling times recorded during the study. From the plasma concentration-time data, the following GSK2857916 (intact and total) PK parameters will be determined as data permit, for each dose of GSK2857916, each schedule and for each subject: After single dose : area under the plasma concentration-time curve (AUC(0-t), AUC (0-tau) and/or AUC(0-∞)), maximum observed plasma concentration (C_{max}), time to C_{max} (t_{max}), last time point where the concentration is above the limit of quantification (t_{last}), systemic clearance (CL), Volume of distribution at steady state (V_{ss}), terminal phase elimination rate constant (λ_z), terminal phase half-life (t_{1/2}). After repeat dose: C_{max} and C_{trough}. For cys-mcMMAF, after single dose, C_{max} and AUC(0-t) will be derived and after repeat dose C_{max} and C_{trough}.

In Part 2 of the study, plasma GSK2857916 concentration-time data together with data from part 1 will be analysed using a population approach. A nonlinear mixed effects model will be used to determine population pharmacokinetic parameters and identify relevant covariates (e.g., age, weight, or disease related covariates). PK parameters will be listed and summarized descriptively (mean, standard deviation, median, minimum, maximum, geometric mean, and the standard deviation, CV% and 95% confidence interval of log-transformed parameters) by dose cohort and schedule in Part 1 and Part 2. To assess the extent of accumulation following GSK2857916 repeat dosing, the observed accumulation ratio (R_o) for both GSK2857916 (intact and total) and cys-mcMMAF will be determined as C_{max} and C_{trough} at steady-state to C_{max} and C_{trough} after the first dose, respectively.

Raw urine Concentrations

Urine concentrations of cys-mcMMAF (part 1 only) will be listed and summarised by GSK2857916 dose, schedule and nominal time range. Plots may also be produced if deemed necessary.

Derived Urine Pharmacokinetic Parameters

If data permits, the following pharmacokinetic parameters will be determined for each GSK2857916 dose, each schedule and for each subject (Part 1 only):

Urinary recovery of unchanged cys-mcMMAF within the 24 h period collection ($A_e(0-24)$) will be calculated. It will be calculated as the product of the concentration in urine and the urine weight, thus assuming a urine density of 1 g/mL.

Fraction of total cys-mcMMAF dose excreted (F_e) in the 24-h interval will be estimated as $A_e(0-24)/(\text{cys-mcMMAF})\text{Dose}$, in the Schedule 1 only (i.e. every 3weeks).

Derived cys-mcMMAF urine pharmacokinetic parameters will be listed and summarised by GSK2857916 dose and schedule.

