1.2.3.2. Repeat dose pharmacokinetics

Rat

The pharmacokinetics of GSK2857916 and cys-mcMMAF has been investigated following IV infusion administration to male and female rats over 3-weeks (once weekly at 3, 10 or 30 mg/kg on Days 1, 8 and 15), followed by a 12-week off-dose period.

Systemic exposure (AUC_{0-168} and C_{max}) increased proportionally with increasing dose and there were no notable differences in the systemic exposure between sexes. The systemic exposure on Day 15 was slightly higher (up to 2.4-fold) than that on Day 1. T_{max} was observed at 0.25 hours, the first sampling point.

The AUC for ADC and total antibody were similar to one another at each dose level on Day 1 and was generally higher for total antibody on Day 15. The C_{max} was generally lower for total antibody than ADC on Day 1, but similar on Day 15. The average half-life was 11 days.

For cys-mcMMAF, there was insufficient data available to determine AUC on Day 1 in the low dose group (3 mg/kg). The systemic exposure increased proportionally with increasing dose and there were no notable differences in systemic exposure between sexes. The systemic exposure on Day 15 was higher (up to 6.4-fold) than that on Day 1. T_{max} ranged from 0.25 to 48 hours.

There were quantifiable concentrations of cys-mcMMAF in the urine samples collected on Day 7, 14, 22, 43R, 64R, 85R and 106R from toxicology animals. The mean total amount of cys-mcMMAF recovered in urine generally increased proportionally with increasing dose of GSK2857916. Cys-mcMMAF was not quantifiable in the urine samples collected on Days -6, -5 and -1 (pre-treatment) at any dose or in control group samples.

Cynomolgus Monkey

The pharmacokinetics of GSK2857916 and cys-mcMMAF has been investigated following IV bolus administration to male and female cynomolgus monkeys over 3-weeks (once weekly at 1, 3 or 10 mg/kg on Days 1, 8 and 15), followed by a 12-week off-dose period.

Gender-averaged systemic exposure increased proportionally with increasing dose and there were no notable differences in the systemic exposure between sexes. The gender-averaged systemic exposure increased 1.2- to 2.1-fold, respectively, from Week 1 to Week 3. Following IV bolus administration of GSK2857916, T_{max} was observed at 0.25 hour (the first sampling time point) in the majority of animals.

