The systemic exposures for ADC and total antibody were similar, with total antibody consistently being slightly higher than ADC. The average half-life was 4 days.

For cys-mcMMAF, the gender averaged systemic exposure (AUC_{0-48hr}) increased proportionally with increasing dose and there were no notable differences in systemic exposure between sexes. The changes in gender-averaged systemic exposure from Week 1 to Week 3 were less than 2-fold. T_{max} was variable, although in most animals T_{max} was achieved within 6 hours after dosing during Weeks 1 and 3.

Table 2 Gender Averaged Pharmacokinetic Values for GSK2857916 (ADC) Following IV Administration to Cynomolgus Monkeys

PK Parameters	AUC ₀₋₁₆₇ ($\mu\text{g}\cdot\text{h}/\text{mL}$)		C _{max} ($\mu\text{g}/\text{mL}$)		T _{max} (h)		t _{1/2} (h)
	Week						
Dose (mg/Kg/week)	1	3	1	3	1	3	3
1	865	1240	22.3	27.5	0.25	0.25	N/A
3	2330	3760	58.8	63.3	0.25	0.25	96.4
10	11200	21500	249	292	0.25	0.25	N/A

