3.8. Dosage and Administration of Study Treatment(s)

GSK2857916 will be administered intravenously over 60 minutes. Subjects enrolled in Schedule 1 will receive one dose every 3 weeks (21 days) for a maximum of 16 cycles (16 doses). Subjects enrolled in Schedule 2 will receive one dose per week for 3 consecutive weeks followed by 1 week rest (28 day cycle) for a maximum of 16 cycles (48 doses).

The maximum dose to be administered to subjects in this trial is 5 mg/kg.

Refer to Section 4 for details on preparation and handling, and administration instructions of GSK2857916.

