19. Collect cytokines at predose (within 30 minutes prior to SOI) and EOI (± 5 min) (even when infusion is interrupted or halted) to assess allergic reaction)
20. All ADA samples will be collected prior to each infusion
21. PK samples to be taken (in all subjects) for both GSK2857916 and cys-mcMMAF measurement: C1D1 at pre-dose (within 30 minutes prior to SOI), 0.5 h after the start of the infusion (SOI) (± 5 min), at the end of infusion (EOI) just before EOI, 1 h after EOI, 3 h after EOI (± 5 min), 8 h after EOI (± 15 min), 24h after EOI (± 1 h) (Day 2); C1D8 1 sample; C1D15 1 sample; C2D1, at pre-dose (within 30 minutes prior to SOI) and at the EOI (just before EOI); C3D1 at pre-dose (within 30 minutes prior to SOI) and at the EOI (just before EOI).
22. Collect 1 PK sample at each subject's final visit.
23. Pre-specified amounts of urine will be collected for PK analysis from the 24 hour urine collection at Screening, C2D1, C4D1, C7D1, C10D1, C13D1, and C16D1. Refer to Section 7.4.2 for details.
24. Study drug administration ± 3 day window only
25. Prophylaxis with prednisolone phosphate 1% or dexamethasone 0.1% 1 drop QID x 4 days starting 1 day prior to treatment
26. Record subject's survival status and whether subsequent treatment for disease was given. Subject does not need to come in for visit.

Abbreviations:

ADA = Antibody Drug Antibody; ALP = alkaline phosphatase; BCVA = best corrected visual acuity; BNP = B-type natriuretic peptide; C1D1 = Cycle 1 Day 1, etc.; cfDNA = Circulating free DNA; CK = creatinine kinase; CRP = C-reactive protein; EM = extramedullary; EOI = End of Infusion; FLC = free light chain; PD = Pharmacodynamics; PK = Pharmacokinetics; QID = 4 times a day; SOI = start of infusion; SPEP = serum protein electrophoresis; UPEP = urine protein electrophoresis

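### In Part 1 the Cmax-based accumulation ratio for cys-mcMMAF sets an end-of-infusion value against a densely sampled first-dose peak, so it is biased low if the peak falls after the infusion ends

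*Protocol*

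**What the plan says.** Section 13.7.3.1 names the catabolite parameters in a sentence that begins "For cys-mcMMAF, after single dose": Cmax and AUC(0-t) after a single dose, Cmax and Ctrough after repeat dosing. The accumulation ratio "for both GSK2857916 (intact and total) and cys-mcMMAF will be determined as" Cmax and Ctrough at steady state over the same quantities after the first dose. Section 13.7.3.2 puts repeat-dose cys-mcMMAF Cmax and Ctrough into the dose-proportionality power model. Section 2 lists repeat-dose Cmax and Ctrough of cys-mcMMAF among the secondary pharmacokinetic endpoints, as data permit.

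Section 3.8 fixes the infusion length: "GSK2857916 will be administered intravenously over 60 minutes". EOI is therefore about 1 h after the start.

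In the Part 1 three-weekly table (Section 7.1.1.1, footnote 21) the first dose is sampled before dosing, at 0.5 h, "just before EOI, 1 h after EOI, 3 h after EOI", then at 8 h and 24 h after EOI and on Days 8 and 15. The repeat doses have two samples each: "C2D1, at pre-dose (within 30 minutes prior to SOI) and at the EOI (just before EOI); C3D1 at pre-dose" and again at EOI. The Part 1 weekly table (Section 7.1.1.2, footnote 22) has the same contrast.

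Section 1.2.3.2 reports that cys-mcMMAF Tmax in rats "ranged from 0.25 to 48 hours". In monkeys it was variable, and in most animals it "was achieved within 6 hours after dosing during Weeks 1 and 3".

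**The concern.** Section 1.2.3.3 describes cys-mcMMAF as a product of ADC catabolism, so its peak need not coincide with that of the parent. At the first dose in Part 1 the schedule can find a delayed peak. At a repeat dose it cannot: the only post-dose sample is taken at about 1 h, and the plan calls that value Cmax. The ratio then has a sampled peak in the denominator and, if the peak is later than EOI, a pre-peak concentration in the numerator.

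The stake is how accumulation of the cytotoxic moiety is reported. Section 1.2.3.2 gives a reason to look: in rats on weekly dosing, cys-mcMMAF exposure rose up to 6.4-fold from Day 1 to Day 15, against up to 2.4-fold for the ADC. A ratio that is low because of the sampling times could be read as absence of accumulation. The population model planned for Part 2 is specified for GSK2857916, so it does not repair the catabolite summary.

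**Working it through.** The protocol states no numerical accumulation ratio, so there is no figure to reproduce. One consistency check is possible. Appendix 10 (Section 16.9.2) allows 10 ml at 5 ml per sample in Cycles 2 and 3 of the Part 1 three-weekly schedule. 10/5 = 2 samples, which agrees with the footnote.

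**Inputs from the protocol.** Infusion 60 min (Section 3.8); sampling times (Section 7.1.1); dosing interval 21 days = 504 h, or 168 h within a weekly cycle; animal Tmax (Section 1.2.3.2); predicted human ADC half-life about 12 days = 288 h (Section 3.6.3.1).

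**Assumptions.** Human Tmax and half-life of cys-mcMMAF are not in the document. I assume a one-dose profile s(t) = exp(-kt) - exp(-ka·t), timed from the start of infusion, with k = ln 2 / half-life and ka solved from Tmax = ln(ka/k)/(ka - k). Doses superpose, and the third dose is compared with the first. Half-lives of 24, 96 and 288 h are shown, the last matching the ADC.

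**Quantities.**
- First-dose Cmax = maximum of s(t) at 0.5, 1, 2, 4, 9, 25, 168 and 336 h.
- Repeat-dose Cmax as the plan would find it = the larger of the pre-dose and 1 h values at dose 3.
- Ratio as written = the second over the first. True ratio = full peak at dose 3 over full peak at dose 1.

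**One case in full** (half-life 96 h, Tmax 6 h, three-weekly). k = 0.00722/h and ka = 0.790/h. First-dose values at 1, 2, 4, 9 and 25 h are 0.539, 0.780, 0.929, 0.936 and 0.835, so Cmax = 0.936. At dose 3 the pre-dose value is 0.027 and the EOI value 0.566. Ratio as written = 0.566/0.936 = 0.60, against a true 1.03. EOI over EOI = 0.566/0.539 = 1.05.

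**Part 1, three-weekly:**

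| Half-life (h) | Tmax (h) | True | As written | EOI over EOI |
|---|---|---|---|---|
| 24 | 1 | 1.00 | 1.00 | 1.00 |
| 24 | 3 | 1.00 | 0.79 | 1.00 |
| 24 | 6 | 1.00 | 0.48 | 1.00 |
| 96 | 1 | 1.03 | 1.03 | 1.03 |
| 96 | 3 | 1.03 | 0.89 | 1.03 |
| 96 | 6 | 1.03 | 0.60 | 1.05 |
| 288 | 1 | 1.39 | 1.39 | 1.39 |
| 288 | 3 | 1.39 | 1.29 | 1.43 |
| 288 | 6 | 1.39 | 1.04 | 1.61 |

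**Part 1, weekly** (three doses 168 h apart, half-life 96 h): a true 1.39 appears as 1.26 at Tmax 3 h and 0.98 at 6 h.

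**Part 2.** The myeloma three-weekly table (Section 7.1.2.1, footnote 24) samples the first dose at pre-dose and EOI only, as it does the later doses. Its ratio is the last column above: equal to the truth or higher. The other three Part 2 tables sample the first dose to 3 h after EOI and repeat doses at pre-dose and EOI. On three-weekly dosing at half-life 288 h they give 1.29, 1.05, 1.08 and 1.85 at Tmax 3, 6, 24 and 48 h, against a true 1.39-1.40. The direction is therefore not constant there.

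**Power model.** If C_EOI = f × Cmax with f the same at every dose, then log C_EOI = log f + a + b·log(dose). The intercept moves and the slope b does not.

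**The case against.** The strongest reply is that nothing here is established for humans. The rat range begins at 0.25 h, the monkey statement gives an upper limit that also covers peaks at or before EOI, and Section 1.3.1 notes that rats are not an antigen-specific species for this drug. If the peak is at EOI there is no bias. This stands, and it makes the finding conditional. It also means that very late peaks should not carry the argument: at Tmax 24 h the model returns 0.11-0.17 for half-lives of 24-96 h, but such peaks rest on the upper part of the rat range and on the minority of monkeys beyond 6 h.

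Several stronger readings are tempting and the documents do not support them:

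- That accumulation is understated throughout the study. The Part 2 myeloma three-weekly cohort, up to 40 subjects, has matched sampling and is not understated.
- That the rule yields a ratio below 1 by construction. At half-life 288 h and Tmax 6 h it gives 1.04.
- That accumulation would be hidden altogether. The Ctrough ratio uses pre-dose samples on both sides, and concentrations are summarized by planned time point, so the EOI values at the first and later doses will both be visible.
- That dose proportionality is biased. No bias in the slope follows unless the EOI fraction changes with dose, and nothing shows that it does.

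Two further defences are weaker. Section 7 lets sampling be moved nearer the peak without an amendment, and the endpoint is qualified by data availability. Neither changes the ratio as defined, and an EOI value will nearly always exist to be labelled Cmax.

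**Conclusion.** The point holds for Part 1, both schedules, and for the Cmax-based ratio of cys-mcMMAF only. As written, that ratio is biased low whenever the peak follows EOI, because the first and repeat doses are sampled differently. The direction follows from the schedule. The size does not, and rests on an assumed one-compartment formation and elimination profile with assumed Tmax and half-life: on three-weekly dosing, from no bias at Tmax 1 h to 0.48-0.60 against 1.00-1.03 at Tmax 6 h (half-life 24-96 h), or 1.04 against 1.39 at half-life 288 h. A post-EOI peak is plausible from the animal data and not shown in humans. No decision rule in the protocol uses this ratio, so the consequence is a misleading pharmacokinetic summary and not a wrong dose decision.

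**What to change.** In Section 13.7.3.1, for cys-mcMMAF:

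- Label the repeat-dose post-dose value C_EOI, not Cmax.
- Form its ratio like for like, repeat-dose C_EOI over C1D1 C_EOI, naming the repeat-dose visit on each schedule. Report it as an EOI ratio and not as peak accumulation.
- Make the Ctrough ratio the main accumulation measure.

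In Section 13.7.3.2, relabel the repeat-dose cys-mcMMAF term C_EOI. It need not leave the power model. Carry the same wording into the reporting and analysis plan.

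No new samples are needed, because the C1D1 EOI sample is already scheduled. The cost is that there will be no peak-accumulation estimate for cys-mcMMAF, which the repeat-dose schedule cannot deliver in any case. The EOI ratio has its own limit: with a long half-life and a late peak it exceeds true peak accumulation (1.61 against 1.39 at 288 h and Tmax 6 h), which is why its label matters. If peak accumulation is wanted, the same post-EOI samples would have to be taken at one repeat dose, at the price of extra blood draws.
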